### **Vigabatrin and Placebo:**

The investigational drug product to be used in this study is vigabatrin, marketed in the US under the trade name Sabril by Lundbeck Pharmaceuticals. Lundbeck will supply vigabatrin for this study directly to the Investigational Pharmacy at Cincinnati Children's Hospital (CCHMC). It is supplied as a white granular powder enclosed in 50x60 mm child-resistant aluminum foil packets (sachet). It is non-hygroscopic, freely soluble in water, and thermodynamically stable with an established shelf life of more than 36 months at room temperature. Povidone is the primary inactive excipient. The investigational pharmacy at CCHMC will produce identical white granular powder with indistinguishable

physical appearance, color, solubility, and taste to the vigabatrin powder supplied by Lundbeck. Both vigabatrin and placebo will be repackaged into identical aluminum foil sachets so as to maintain treatment blinding and distribute as appropriate to the investigational pharmacies at local participating sites for individual patient distribution and administration. For administration, the entire content of one sachet (500 mg active drug) is dissolved in 10 ml water for oral administration that is dosed according to body weight 50-150 mg/kg/day divided BID. Dosing will follow established recommended guidelines (50 mg/kg/day and increased as needed by 50 mg/kg/day every 3 days up to a maximum dose of 100 mg/kg/day, divided BID in the blinded phase and 150mg/kg/day in the Open Label Phase).

Subjects randomized to vigabatrin in Arm A (Figure 1) will be treated with vigabatrin 100mg/kg/day or placebo until 24 months of age or until they show evidence of clinical seizures or electrographic seizures on video EEG. Based on the published EEG biomarker data for infants with TSC, the subjects randomized to our primary randomized trial population, Arm A (who have evidence of epileptiform activity in their EEG) will be at high risk for developing epilepsy (approaching 100%).

If the subjects in Arm A are seizure free at 24 months of age, they will be tapered off the study drug (vigabatrin or placebo) without breaking the treatment blind and continue to be followed for the duration of the study (36 months).

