If electrographic or clinical seizures occur while on study drug, they will transition into the Open label phase of the study (Arm B) and continue to be followed until 36 months of age as per the PREVeNT protocol schedule. If the seizures are not controlled in the Open label phase at the vigabatrin maximum dose of 150mg/kg/day, the investigator may change the antiepileptic medication as clinically warranted to improve seizure control (including tapering off vigabatrin). These subjects will remain in the open arm of the study for the duration of the protocol (36 months).

Based on the TSC-EBS data, it is estimated that 30% of subjects (24 subjects) in Arm C will not be treated but continue in the study until the age of 36 months (Table 2).

See Pharmacy Manual for details of packaging and labeling, product tracking and accountability, and product disposal and destruction.

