A second consideration is the observation time during the trial. Since the patients will be put on active therapy following an event, a second consideration is the duration of seizure suppression, that is, the time after an event has occurred up until two years. This is effectively, the medication possession ratio ( $MPR = \text{total time on vigabatrin treatment} / \text{total follow-up time}$ ). We expect the delayed treatment group on average to have Vigabatrin treatment for slightly less than 1-2 years and effectively 2-3 years for early treatment group. This is based on assuming a uniform distribution of occurrence of the clinical seizures. Clearly, if there were no significant differences between the early and late treatment in this parameter, we would expect a negative outcome. However, this parameter may be useful in understanding the extent of the differences observed. The MPR, if there is a relationship to the primary outcome, may be useful for imputation of missing data (which we expect to be quite low). This variable can be entered into the cLDA model and assessed using the procedures of MacKinnon for testing mediation. The mediation model would say that the effect of the treatment on the outcome of the cognitive scores is mediated through the MPR and not the earlier intervention. The sample size may not allow a clear answer to this question, but if earlier intervention before the onset of a clinical seizure is key in preservation of cognitive function, then the mediation will not be demonstrated.

Drug resistant epilepsy: For the current study, drug resistant epilepsy is defined as the “failure of adequate trials of two tolerated appropriately chosen and used antiepileptic drug schedules (whether as monotherapy or in combination) to achieve sustained seizure freedom as put forth by the International League Against Epilepsy. This will be compared between the early and delayed treatment groups using Fisher’s exact test.

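### The early-arm exposure forecast conflicts with the protocol's own treatment rules, the medication possession ratio has no clear end point, and a failed mediation test would say little about early timing

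*Combined protocol and SAP*

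**What the plan says.** The Analyses section offers drug exposure as a second consideration when interpreting the cognitive result. It introduces the quantity as "the time after an event has occurred up until two years" and equates it with a medication possession ratio: time on vigabatrin divided by total follow-up. It expects the "delayed treatment group on average to have Vigabatrin treatment for slightly less than 1-2 years" and "effectively 2-3 years for early treatment group", adding: "This is based on assuming a uniform distribution of occurrence of the clinical seizures". If the arms do not differ significantly on this parameter, it expects a negative trial.

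The ratio may be entered in the longitudinal model and tested for mediation. Mediation would mean that the cognitive effect runs through the ratio and not through the earlier start. The plan concedes that the sample may be too small for a clear answer, then says that "if earlier intervention before the onset of a clinical seizure is key in preservation of cognitive function, then the mediation will not be demonstrated".

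The treatment rules are elsewhere. Vigabatrin and Placebo says: "If the subjects in Arm A are seizure free at 24 months of age, they will be tapered off the study drug". Protocol description says the same. Children who seize move to open-label vigabatrin, which may later be changed or tapered, and "continue to be followed until 36 months of age as per the PREVeNT protocol schedule". The earliest baseline visit in Appendix 2, Table 1 is at about 6 weeks of age. The primary outcome is the Bayley-III cognitive score at 24 months of age.

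**The concern.** Three things do not fit together.

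- **Exposure.** A child who starts after birth and stops at 24 months of age cannot accumulate 2-3 years of drug.
- **Window.** One description of the ratio ends at two years. The other divides by follow-up that continues for a year after the primary outcome. Exposure after 24 months cannot mediate a 24-month score. In that year seizure-free early-arm children are off drug, while delayed-arm children who seized may still be on it, so the contrast between arms shrinks.
- **Interpretation.** The only prediction attached to the early-timing account is that mediation will not be shown. A small trial often produces that result whatever the mechanism.

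Whether benefit comes from starting early or from longer exposure matters for the Phase III design that this trial is meant to inform. A null mediation result could be given more weight there than it can bear.

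**Working it through.** **Inputs from the documents.** Seizure rates are 22/24 on placebo and 5/24 on vigabatrin, or 10/24 in the pessimistic case. Seizure onset is uniform. There are 24 children per arm and the effect size is 0.885 SD. Treatment ends at 24 months of age if seizure free. Follow-up ends at 36 months.

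**Assumptions not in the documents.** Age at randomisation *r* (months) varies over the ranges shown, adherence is full, and the residual SD is 1.

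**1. Reproducing the plan's figures.** If every delayed-arm child seizes, mean exposure is (24 − r)/2 months to age 24 and 12 + (24 − r)/2 to age 36.
- r = 0: 1.0 and 2.0 years.
- r = 1.5: 0.94 and 1.94 years.

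So the delayed-arm figure reproduces, apparently as a pair for the two horizons. The early-arm pair of 2 and 3 years needs 24 − 0 and 36 − 0 months: treatment from birth and no stop at 24 months.

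**2. Exposure under the protocol's rules (years).** In the early arm, exposure to age 24 months is (24 − r)/12. If a fraction q seize and stay on drug, the mean to age 36 is (24 − r + 12q)/12. The delayed arm uses 22/24 seizing.

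| r (months) | Early to 24 | Early mean to 36, q = 5/24 | Early mean to 36, q = 10/24 | Delayed to 24 | Delayed to 36 |
|---|---|---|---|---|---|
| 1.5 | 1.875 | 2.08 | 2.29 | 0.86 | 1.78 |
| 6 | 1.50 | 1.71 | 1.92 | 0.69 | 1.60 |
| 12 | 1.00 | 1.21 | 1.42 | 0.46 | 1.38 |

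The longest possible exposure to age 36 is 36 − 1.5 = 34.5 months, or 2.875 years. The visit windows (1 week early, 2 weeks late) add at most 3/52 = 0.06 year, giving 1.93 and 2.93, still below 2 and 3. At r = 6 the gap between arms is 1.50 − 0.69 = 0.81 year to age 24, but 1.71 − 1.60 = 0.11 year to age 36.

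**3. The ratio under each window.** Take r uniform on 3-12 months. To age 24 the early arm has ratio 1 and the delayed arm 22/24 × 0.5 = 0.46. For age 36, let k be the mean of 12/(36 − r), which is 12 × ln(33/24)/9 = 0.425. Let c be the fraction of children who seized and continue vigabatrin from 24 to 36 months.
- Early: (1 − k) + (5/24)ck
- Delayed: (22/24)[(1 − k)/2 + ck]

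| Window | Early | Delayed | Gap |
|---|---|---|---|
| To 24 months | 1.00 | 0.46 | 0.54 |
| To 36, all continue (c = 1) | 0.66 | 0.65 | 0.01 |
| To 36, half stop at 24 (c = 0.5) | 0.62 | 0.46 | 0.16 |
| To 36, all stop at 24 (c = 0) | 0.58 | 0.26 | 0.31 |

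With 10/24 seizing on vigabatrin and all continuing, the ratios to 36 months are 0.75 v 0.65.

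**4. How often mediation is shown.** In simulated trials (2,000 per setting) the 24-month ratio carried the whole effect, with slope 0.885/0.542 = 1.63 SD per unit of ratio. The test was Sobel's.
- 24-month ratio: mediation shown in about 65%, missed in about 35%.
- 36-month ratio, half or more of those who seized continuing: shown in about 0-11%, missed in about 89-100%. A joint-significance test misses less often when half stop: a re-run found mediation in roughly 19-25%.
- 36-month ratio, all stopping at 24 months: shown in about 60% in the re-run, close to the 24-month ratio.
- 24-month ratio carrying half the effect: missed in about 79%. Carrying none: not shown in about 98%.

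With the 24-month ratio, then, a null result favours pure timing over full mediation by 98/35 = 2.8, and over half mediation by only 98/79 = 1.2.

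**5. Seizure age.** Under full adherence the early arm's 24-month ratio is constant at 1. All within-arm variation is in the placebo arm, where an early seizure gives a high ratio. If earlier seizures also cost 0.5 or 1.0 SD per 12 months (an assumption), detection of full mediation with the 24-month ratio falls from about 66% to 27% or 4%.

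**The case against.** The strongest reply is that this analysis is optional, comes with an explicit sample-size caveat, and touches neither the primary longitudinal comparison nor the seizure test. That is correct and limits the importance of the point. The two-year phrase also suggests that the authors may already intend a 24-month ratio. That is a fair reading, but the definition that follows says otherwise. Because the longitudinal model includes 36-month scores, a longer window is not absurd for that contrast.

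Four stronger readings are tempting and not supported.

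- **The analysis favours early timing whatever the truth.** It does not. With a 24-month ratio and no confounding, it goes against the timing account in about two thirds of trials when exposure carries the whole effect.
- **The plan will treat failed mediation as proof of timing.** The text runs the other way, from timing to non-demonstration. The converse is invited by the absence of any other prediction, but it is not written.
- **Both exposure figures are impossible.** The delayed-arm figures reproduce. To age 36 months, early-arm children who seize and stay on drug can exceed 2 years, and the arm mean can pass 2 with very early randomisation or more seizures.
- **The 36-month ratio guarantees no difference.** That needs nearly all children who seize to continue vigabatrin. The protocol allows tapering or a change of drug, and the gap is 0.16 if half stop and 0.31 if all stop at 24 months.

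**Conclusion.** The point holds in limited form. The early-arm forecast contradicts the start age and the 24-month taper: at most 1.875 years before the primary outcome on the visit schedule, and less than 3 years at any horizon. The ratio's window is ambiguous, and the choice moves the expected gap between arms from 0.54 to somewhere between 0.01 and 0.31 at the plan's seizure rates. If most children who seize continue the drug, the plan's remark that no difference in the ratio predicts a negative trial would mislead, because the ratios could match while the drug worked as planned.

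Non-demonstration of mediation cannot support early timing at this sample size. It occurs in about 35% of trials under full mediation with the 24-month ratio. With the 36-month ratio it occurs in about 89-100% by the Sobel test when half or more of those who seize continue. The exposure ceilings follow from the protocol. The ratios and detection rates rest on the assumed randomisation ages, full adherence and unit residual SD. The loss from seizure-age confounding rests on an assumed penalty, so only its direction is secure.

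**What to change.** - Define the ratio from randomisation to the 24-month Bayley.
- Reconcile the exposure forecast in Analyses with the taper rule in Protocol description and in Vigabatrin and Placebo. If those rules stand as written, give early-arm exposure to the primary outcome as 24 months minus age at randomisation (below about 1.9 years), with the expected mean shown as a range over assumed randomisation ages.
- Report the indirect effect with a bootstrap confidence interval. Resampling methods for indirect effects are already among the plan's references.
- Replace the closing sentence on mediation with a statement that failure to show mediation is inconclusive and is not evidence for early timing.
- Do not make adjustment for seizure occurrence and timing the main analysis. It removes most of the placebo-arm variation in the ratio, cutting detection of full mediation from about 65% to 34% in simulation, and it conditions on the plan's own proposed mechanism. At most it is a sensitivity analysis.

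The cost is SAP wording, using data already collected. The downside is that the mediation analysis will support a weaker conclusion.

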For the accurate identification of clinical seizures, parents and caregivers will review a seizure recognition video at the time of study enrollment and retain it as a reference throughout the study. They will also be encouraged to video any suspicious events during the study period for review by clinicians of the investigation team. If at any point during the study the subject is suspected of having a clinical seizure, the parents/caregiver will be instructed to contact their site's study coordinator. The subject will be seen as soon as possible for a study visit and a video EEG will be completed for confirmation of clinical or electrographic seizure onset. Those subjects with either a documented clinical seizure on video or evidence of an electrographic seizure on video EEG will be transitioned to the Open-Label treatment phase.

At the emergence of abnormal epileptiform activity (*i.e.* sharp waves, spikes or polyspikes, spike and wave discharges, classic or modified hypsarrhythmia) prior to the onset of the first clinical or electrographic seizure, subjects will enter the protocol blinded-treatment phase (Arm A). Emergence of these specific, predetermined EEG biomarkers detected by video EEG will lead to a 1:1 randomization with vigabatrin or placebo. The vigabatrin and placebo will be dispensed as a sachet and those subjects randomized to vigabatrin will be titrated up to 100mg/kg/day by 50mg/kg/day every 3 days during the blinded phase of the study. The research pharmacist at each site will be unblinded during this phase of the study and the vigabatrin and placebo sachets doses will be identical in order to maintain the blind.

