### Primary Study Objective:

The primary endpoint of this Phase IIb feasibility trial will be the demonstration of the prevention of seizures and the subsequent cognitive assessment component of the Bayley-III. The other components of the Bayley (receptive communication, expressive communication, fine and gross motor subscores) will be used as secondary and supportive endpoints. The primary goal of this Phase IIb trial will be to provide the evidence needed for a Phase III pivotal trial. Thus, the study will need to demonstrate the purported mechanism by which an improved clinical outcome is achieved, prevention of seizures, leading to a difference in cognitive outcomes. The rationale for not using a composite outcome at this stage of evaluation is that it will be simpler to focus on a single most promising outcome measure of early treatment and one that is clinically meaningful. The other components of the Bayley-III will be evaluated in a multivariate composite as part of the secondary outcomes and exploratory outcome.

The sample size for this feasibility trial is derived from the resources available to support the trial as per this NINDS mechanism, the primary goal of demonstrating a reduction in seizures and the power to assess the differences in cognitive scores on the Bayley-III. To assess the plausibility of recruitment, we looked at the pilot data from our ongoing TSC

Project. To date, we have enrolled 40 patients, 1 patient dropped out; 15 continue without seizures to date; 19 developed well controlled seizures, and 5 have developed refractory seizures. Thus, 25 of the 40 or almost two thirds of the enrolled patients have developed seizures to date. Reducing this number with earlier intervention would seem consistent with achieving a positive effect on the cognitive outcomes as assessed by the Bayley-III.

[figure not shown]
[figure not shown]
[figure not shown]
[figure not shown]
We expect to be able to recruit between 75 and 80 participants over the course of the recruitment period. Based on these numbers we expect 37.5% (based on our P20 data where 15/40 remained seizure free) to be biomarker free and never randomized. Thus, we expect to lose to randomization between 28 to 30 participants yielding approximately 48 patients to be randomized ( $75-28 = 47$  and  $80-30=50$ ) or 24 to 25 participants per group.

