## Early Global Development in Tuberous Sclerosis

In addition, for the cognitive outcomes, using a t-test on the final Bayley-III Cognitive Scores shows that when the sample size is 24 participants per arm there is 85% power to detect an effect size on the cognitive component of the Bayley III of 0.885 when the Type I error is 0.05, two tailed. The plausibility of achieving this effect size was assessed using published data from the Bayley III manual. In children with Pervasive Developmental Disorders, the average cognitive score is 5.7 (sd 2.9) compared to matched controls with a mean of 11.0 (sd 3.0). The effect size for the difference between this disorder and the matched controls is 1.77  $[(11.0-5.7)/3.0]$ , a difference double the effect size detectable with the sample size available for this Phase IIb trial. While it is unlikely that early treatment would return these patients to normal levels, we are hypothesizing as the alternative that we will achieve an effect size of approximately 50% of the difference compared to normal scores. That is, we will use a sample size necessary to detect an effect size of 0.885.

To further examine the ability of the sample size to achieve the goals of the study, we first examined the sensitivity of the design to our assumption of the standard deviation by examining the standard deviation against other groups of special interest.

The Bayley-III cognitive test battery shows that the standard deviations vary from a low of 1.9 at an assessment in Downs Syndrome Children to 3.5 amongst SGA infants. The table below shows the standard deviations for various special groups.

PDD	CP	DD	Language impaired	Perf At Risk	Asphyx	Fetal Alcohol	SGA	Premie
2.9	3.1	1.9	2.4	3.2	3.1	2.7	3.5	3.1

The average standard deviation is 2.9, the median is 3.1, so again, using 3.0 in our calculations seemed reasonable.

We next estimated the sensitivity of the trial in terms of the power for testing the time-averaged difference (TAD) between two means in a *repeated measures* design. In the TAD model, we assumed the mean difference starts to become evident at 3 months and is continuing or enlarging at 12, 24 and 36 months. The correlation amongst Bayley-III Cognitive assessments within person was varied from 0.10 to 0.80.

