Additional developmental measures and ASD Risk: The sub-scores on the Bayley-III and the composite score estimated using Hotelling’s  $T^2$ . The power for this endpoint will vary, but is expected to be similar to the primary. In the children with Pervasive Developmental Disorders, the effect sizes versus normal matched controls were 1.77, 1.67, 1.17 and 1.33 for the Receptive communication, Expressive Communication, Fine and gross motor sub-scores respectively. The ADOS2 will be completed at 24 and 36 months of age as a neurodevelopmental assessment for symptoms of ASD. The results from Study Arm A (seizure free, no treatment), Arm B (VGB versus. Placebo), and subjects with electrographic seizures at baseline EEG who move directly into Open Label treatment will be compared increasing our power to assess differences (Figure1).

Determination of vigabatrin safety as a preventative treatment for clinical seizures in infants with TSC will be assessed using comparison between the treatment groups and as a summary of exposure time on the drug. The outcome measure will be percentage of patients in each group (vigabatrin early treatment vs. vigabatrin delayed treatment) with treatment associated adverse events (AEs), serious adverse events (SAEs), and risk evaluation and mitigation strategy (REMS) measures. Treatment related AEs and SAEs will be monitored and tabulated. Given the expectation that the delayed group will cross-over to active treatment sooner than the early treatment group, adverse events will be characterized using life table approaches to ensure adjustment for exposure time. Thus, counts of individuals with AEs, total number of specific AEs and rate per months of follow-up will all be provided and assessed for any differences and for the safety population (early plus late on person years of exposure basis). Events of specific interest and risk evaluation and mitigation strategy (REMS) measures will be compared, including any and all ophthalmologic problems that may arise. Data from the negative control group (estimated to be approximately 15-20 patients) will also be used to compare the occurrence of AEs and SAEs.

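### Under the plan's own 50% effect rule, the two Bayley-III motor sub-scores have about 51% and 62% power, which is not similar to the primary's 85%

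*Combined protocol and SAP*

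**What the plan says.** The paragraph on additional developmental measures and ASD risk (Analyses) names the Bayley-III sub-scores and a composite tested with Hotelling's T-squared. It then says: "The power for this endpoint will vary, but is expected to be similar to the primary". The only support offered is a list of effect sizes comparing children with Pervasive Developmental Disorders with matched normal controls: "1.77, 1.67, 1.17 and 1.33 for the Receptive communication, Expressive Communication, Fine and gross motor sub-scores respectively".

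The primary's power is given under Early Global Development in Tuberous Sclerosis, "using a t-test on the final Bayley-III Cognitive Scores": "when the sample size is 24 participants per arm there is 85% power to detect an effect size" of 0.885, "when the Type I error is 0.05, two tailed". That effect size is derived from the same kind of comparison. The cognitive gap between the disorder group and controls is 1.77. The plan calls a full return to normal unlikely and takes as its alternative that "we will achieve an effect size of approximately 50% of the difference compared to normal scores", that is 0.5 × 1.77 = 0.885.

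No power figure, treatment-effect fraction or inter-score correlation is stated for the sub-scores or the composite.

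**The concern.** The primary reaches 85% because its gap of 1.77 is large enough that half of it is 0.885. The gaps printed for fine motor (1.17) and gross motor (1.33) are smaller. If treatment is assumed to close the same share of each gap, these two scores cannot have similar power at the same sample size. A power statement should follow from the figures set beside it, and for two of the four scores this one does not appear to.

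What is at stake is limited. The sub-scores belong to secondary objective 2 and are described as supporting the primary. The risk is that a reader takes a non-significant motor result as coming from a comparison with roughly 85% power.

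**Working it through.** **Inputs**

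- Two-sample t-test, two-sided alpha 0.05, 24 per arm (Early Global Development in Tuberous Sclerosis).
- Recruitment expectation "or 24 to 25 participants per group" (Primary Study Objective, statistical section); allocation "will lead to a 1:1 randomization with vigabatrin or placebo" (protocol description, after the exclusion criteria).
- Gaps to normal: receptive 1.77, expressive 1.67, fine motor 1.17, gross motor 1.33 (Analyses).
- Treatment closes 50% of the gap. This is stated for the cognitive score; carrying it over to the sub-scores is an inference.
- No dropout, as in the plan's own figure.

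**Formula.** For standardized effect d and n per arm, the noncentrality is d × √(n/2) on 2n − 2 degrees of freedom. Power is the probability that the noncentral t exceeds the critical value in absolute size. With n = 24, √12 = 3.464, df = 46 and the critical value is 2.013.

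**Step 1: reproduce the primary.** d = 0.885 gives noncentrality 0.885 × 3.464 = 3.066 and power 85.1%. The plan says 85%, so the method matches.

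**Step 2: apply the same calculation to half of each printed gap.**

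| Sub-score | Printed gap | Half | Noncentrality | Power, 24 per arm | Power, 25 per arm |
|---|---|---|---|---|---|
| Receptive communication | 1.77 | 0.885 | 3.066 | 85.1% | 86.6% |
| Expressive communication | 1.67 | 0.835 | 2.893 | 80.8% | 82.5% |
| Gross motor | 1.33 | 0.665 | 2.304 | 61.6% | 63.5% |
| Fine motor | 1.17 | 0.585 | 2.026 | 51.0% | 52.7% |

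At 24 per arm the shortfall against the primary is 85.1 − 61.6 = 23.5 points for gross motor and 85.1 − 51.0 = 34.1 points for fine motor. Using the normal approximation at 24 per arm instead, the motor powers are 63.5% and 52.7%, so the choice of method does not matter.

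**Step 3: what would make the motor scores similar.** To reach d = 0.885, treatment would have to close 0.885/1.33 = 67% of the gross motor gap and 0.885/1.17 = 76% of the fine motor gap. At half the gap, 85% power would need about 42 per arm (gross) or 54 per arm (fine).

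**Step 4: the composite.** With p = 4 scores and total N = 48, Hotelling's T-squared has noncentrality (n/2) × d′R⁻¹d, on 4 and N − p − 1 = 43 degrees of freedom. R is the correlation matrix of the scores. The documents give no R, so one common correlation ρ is assumed here.

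| ρ (assumed) | 0 | 0.2 | 0.3 | 0.5 | 0.7 | 0.9 |
|---|---|---|---|---|---|---|
| Power | 99% | 90% | 85% | 75% | 71% | 83% |

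Power falls and then rises again as ρ grows, so a range quoted for the composite depends on which correlations are chosen.

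**The case against.** Four points can be made for the plan.

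- **The sentence may concern only the composite.** It speaks of one endpoint and follows directly on Hotelling's T-squared; the statistical section on the primary objective also says that the other components go into a multivariate composite. This reading is possible. The motor figures would not then contradict the sentence, and composite power does reach the primary's level at some correlations. But the preceding sentence names the sub-scores as well, and four separate effect sizes follow. Even on this reading the claim lacks the correlation it depends on.
- **The printed effect sizes do not themselves give 51% and 62%.** This is correct, and a reader might wrongly infer that they do. Used in full, 1.17 and 1.33 give about 98% and 99%. The lower figures appear only after halving, under a rule stated for the cognitive score. That rule is nevertheless the only one the plan offers. Using the full gaps would assume the return to normal that the plan calls unlikely, and would put the primary near 100% too.
- **The plan says that power will vary.** It does, and it prints the differing effect sizes openly. But the same sentence concludes that power is similar, and a shortfall of 23 to 34 points is more than that wording can cover.
- **These are secondary outcomes in a feasibility trial sized by available resources.** This stands. They need not be powered at 85%; the point is only that a stated power should follow from its own figures.

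**Conclusion.** The power statement is too favourable for two of the four sub-scores. With 24 per arm, two-sided 0.05 and half of each printed gap, power is about 62% for gross motor and 51% for fine motor, against 85% for the primary. It is fair for receptive communication (85%) and expressive communication (81%). This rests on carrying the 50% rule over from the cognitive score and on reading the sentence as covering the separate sub-scores. If it covers only the composite, it is neither right nor wrong until a correlation structure is stated.

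Two stronger conclusions should not be drawn. First, a reader might infer that the Phase III decision is compromised. The Analyses section ties the go decision to seizures and to the standardized cognitive scores, not to the motor scores, and the primary sample size is untouched. Second, a reader might infer that the plan intends to treat a null motor result as a well-powered negative. Nothing in the documents says so; that is a possible misreading, not a stated use. This is a minor correction of wording.

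**What to change.** Replace the sentence with the four sub-score powers at 24 per arm and two-sided 0.05: receptive communication about 85%, expressive communication 81%, gross motor 62% and fine motor 51%. State that they assume treatment closes half of each printed gap to normal, as for the cognitive score.

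For the composite, either give its power with the assumed correlation structure labelled as an assumption, or make no power claim for it.

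The change is confined to that power statement. No test, sample size or decision rule changes. The only cost is a less favourable stated power for two secondary sub-scores.
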